3.3.3 Discontinuation from Study Participation

Study participation by an individual subject must be prematurely discontinued for any of the following reasons:

- The subject withdraws consent or requests discontinuation for any reason.
- Occurrence of any medical condition or circumstance that exposes the subject to substantial risk and/or does not allow the subject to adhere to the requirements of the protocol.
- Any SAE, clinically significant adverse event, severe laboratory abnormality, intercurrent illness, or other medical condition which indicates to the Investigator or Sponsor that continued participation is not in the best interest of the subject.
- Subject failure to comply with protocol requirements or study-related procedures.

If a subject withdraws prematurely from the study, study staff should make every effort to contact the Sponsor prior to discontinuation, if possible, and to complete the full panel of assessments scheduled for the Early Termination Visit. The reason for subject withdrawal must be documented in the electronic Case Report Form (CRF).

In the case of subjects lost to follow-up, attempts to contact the subject must be made and documented in the subject's medical records.

The SSRC may recommend enrolling more than 12 subjects into a cohort (Cohort 1, 2, and/or 3) to allow adequate data collection for assessment of cohort progression and/or study objectives. Expansion of a given cohort, if needed, will not affect the size of subsequent cohort(s).

3.4 Early Termination Visit and Withdrawal Procedures

For subjects who are withdrawn from the study prior to completion of the study, the subject should return for an Early Termination Visit. The reason for subject withdrawal from the study must be documented in the eCRF.

4 TREATMENTS ARMS

The following treatment arms and dosing regimens are planned.

4.1 Treatment Groups

Subjects entering Cohort 1 will be randomized to 1 of 2 treatment arms in a ratio of 2:1 (MAU868:placebo):

- MAU868 1350 mg every 28 days for a total of 4 doses
- Placebo every 28 days for a total of 4 doses.

Subjects entering Cohort 2 will be randomized to 1 of 2 treatment arms in a ratio of 2:1 (MAU868:placebo):

- MAU868 6750 once and 1350 mg every 28 days for a total of 4 doses
- Placebo every 28 days for a total of 4 doses.

Subjects entering Cohort 3 will be randomized to 1 of 2 treatment arms in a ratio of 2:1 (MAU868:placebo):

- MAU868 6750 mg every 28 days for a total of 4 doses
- Placebo every 28 days for a total of 4 doses.

Minimum duration of the infusion for 6750 mg is at least 180 minutes and for 1350 mg is at least 60 minutes. All infusions will be followed by at least a 25 mL D5W flush to run at the same infusion rate as the dose of study drug.

A Pharmacy Manual will provide instructions for preparation of the infusion. The study drug is prepared as a dilution of the 450 mg/3mL stock solution in a total volume of 250 mL D5W. The investigational product is to be stored at 2° to 8° Celsius, protected from light and not shaken.

4.2 Randomization

Study participants will be randomly assigned to their treatments. Two participants will be assigned to receive treatment with MAU868 for each participant assigned to receive treatment with placebo (2:1 randomization). Randomization will occur via an Interactive Web Response System (IWRS). The Investigator or delegate will contact the IWRS after confirming that a potential study participant is eligible. The IWRS will assign a randomization number that will be used to link the subject to a treatment arm.

The randomization number is only used to identify which treatment study participants have been assigned to receive. The number assigned to a subject at screening remains the unique identifier for the subject throughout the study. For information on subject numbering, please see “Subject numbering” section in the IWRS manual. The randomization numbers will be generated using procedures that ensure that treatment assignment is unbiased and concealed from the Sponsor, subjects, and Investigator staff. A subject randomization list will be produced by a CRO.

The randomization scheme for subjects will be reviewed and approved by the Sponsor.

Follow the details outlined in the IWRS Manual regarding the process and timing of treatment assignment and randomization of subjects.

4.3 Treatment Arm Blinding

This is a subject, Investigator, and Sponsor-blinded study. Subjects and Investigators will remain blinded to study treatment arm (MAU868 or placebo) throughout the study.

Drug product will be supplied in bulk, so an unblinded pharmacist, or appropriately designated study site staff who is independent of the study team, will be required in order to maintain the blind. This unblinded associate at the site will be notified by the IWRS that a subject is randomized and to which treatment arm, which will then enable and instruct them to prepare the study drug.

4.3.1 Breaking the Treatment Blind

Blinding is critical to the integrity of this clinical study. However, in the event of a medical emergency or pregnancy in an individual subject, in which knowledge of the investigational product is critical to the subject’s management, the Investigator should contact the Medical Monitor to review the situation prior to breaking the blind.

Before breaking the blind of an individual subject’s treatment, the Investigator should have determined that the information is necessary (i.e., that it will alter the subject’s immediate management). In many cases, particularly when the emergency is clearly not investigational product related, the problem may be properly managed by assuming that the subject is receiving active product without the need for unblinding.

When the Investigator contacts the system to break a treatment code for a subject, he/she must provide the requested subject identifying information and confirm the necessity to break the treatment code for the subject. The Investigator will then receive details of the investigational drug treatment for the specified subject via the IWRS. The system will automatically inform the study monitor for the site and the Study Team that the code has been broken.

It is the Investigator's responsibility to ensure that there is a dependable procedure in place to allow access to the IWRS /code break at any time in case of emergency.

An assessment will be done by the appropriate site personnel and Sponsor after an emergency unblinding to assess whether or not study drug should be discontinued for a given subject.

In cases of accidental unblinding, contact the Medical Monitor and ensure every attempt to preserve the blind is made.

5 DRUG SUPPLIES

5.1 Formulation and Packaging

There is no administration kit. A disposable syringe will be used to withdraw the contents of the vial.

MAU868

MAU868 450 mg/3 mL (150 mg/mL) solution for infusion and injection is a slightly opalescent and colorless to slightly colored aqueous solution packaged in a 6 mL clear glass vial with a grey rubber stopper, which is sealed with an aluminum cap with plastic flip-off disk. The vial is overfilled by 10% (containing a total volume of 3.3 mL) to allow for the complete removal of the dose (450 mg).

MAU868 450 mg/3 mL solution for infusion and injection contains, in addition to MAU868 drug substance, L-histidine, L-histidine-hydrochloride monohydrate, sucrose and polysorbate 20. The excipients utilized are standard pharmacopeial grade excipients that are commonly used in antibody parenteral products. The formulation does not contain any preservative; it is to be used for single-dose administration only.

Placebo

Placebo solution D5W will be supplied by the clinical site.

5.2 Study Drug Preparation and Dispensing

MAU868 will be administered via IV infusion. Refer to the Pharmacy Manual for dose preparation and administration instructions.

5.3 Study Drug Administration

Study drug should be administered only at clinical sites. All clinical sites must have the appropriate equipment and trained personnel needed to effectively manage hypersensitivity reactions including anaphylaxis and infusion reactions.

Cohort 1 MAU868 Arm:

- MAU868 1350 mg IV over at least 60 minutes approximately every 28 days for a total of 4 doses.

Cohort 2 MAU868 Arm:

- MAU868 6750 mg IV over at least 180 minutes on Study Day 1, then 1350 mg IV over at least 60 minutes for subsequent doses approximately every 28 days for a total of 4 doses.

Cohort 3 MAU868 Arm:

- MAU868 6750 mg IV over at least 180 minutes approximately every 28 days for a total of 4 doses.

Placebo

- Cohort 1: Placebo (D5W) will be administered as an IV infusion over at least 60 minutes approximately every 28 days for a total of 4 doses.
- Cohort 2: Placebo (D5W) will be administered as an IV infusion over at least 180 minutes on Day 1 and then over 60 minutes approximately every 28 days for a total of 4 infusions.
- Cohort 3: Placebo (D5W) will be administered as an IV infusion over at least 180 minutes approximately every 28 days for a total of 4 infusions.
- Placebo is prepared as a standard 250 mL volume of intravenous fluid.

All infusions will be followed by at least a 25 mL D5W flush to run at the same infusion rate as the dose of study drug.

Refer to the Pharmacy Manual for additional dose preparation and administration instructions.

5.3.1 Dose Adjustments and Interruption of Study Drug

Dose adjustments and interruptions of study drug are not permitted. Interruptions of individual infusions, however, are permitted in the event venous access becomes compromised or a subject is not tolerating the infusion ([Section 7.3.1](#)). The details of any interruption of an infusion, including the reason(s), the timing, and the resumption and completion of the infusion if applicable, must be recorded in the source documents and the eCRF.

For subjects who may require a hemodialysis, plasmapheresis, or immunoabsorption treatment, it shall be assumed that the study drug has been removed. A blood sample for PK analysis should be collected prior to and following these treatments. In the event that a subject requires hemodialysis, plasmapheresis, or immunoabsorption treatments; if <15 days since last MAU868/placebo treatment another dose will be given as soon as possible, and the next scheduled monthly dose skipped. Regular dosing will occur the following month. If the last dose was 15 days or greater no interim dose will be administered, and the regular monthly schedule will be followed. No subject will receive more than 4 doses. Subjects anticipated to require hemodialysis, plasmapheresis or immunoabsorption treatment at the time of randomization should not be randomized ([Exclusion Criterion 5](#)).

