From a safety perspective, the highest administered dose of MAU868 expected in this study (6750 mg = 100 mg/kg for a 67.5 kg patient) was also the highest administered dose (MAU868 100 mg/kg) investigated in the first-in-human study and below the no observed adverse effect level (NOAEL) exposure (750 mg/kg) in the 4-week repeat-dose toxicity study in rats. Specifically, human steady-state AUC exposure at the proposed dose of MAU868 1350 mg (20 mg/kg for a 67.5 kg patient) once monthly (206231 µg·hr/mL) provides safety margins of 6.9X and 5.0X, respectively, compared to the NOAEL (750 mg/kg; 1420000 µg·hr/mL) in the 4-week rat study and to the AUC at the highest human dose (100 mg/kg; 1031155 µg·hr/mL) tested to date. Likewise, human steady-state AUC exposure at the proposed dose of MAU868 6750 mg once monthly (1031155 µg·hr/mL) provides a safety margin of 1.4X compared to the NOAEL (750 mg/kg; 1420000 µg·hr/mL) in the 4-week rat study.

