3. During the follow-up period, if the subject cannot be seen on the precise protocol-defined study day, the acceptable visit window is +/-10 days.
4. Study Day 1 is the calendar day on which the first dose of study drug is administered. Subsequent study days are based on calendar days.
5. The information necessary for determining the KDPI includes *donor* age, height, weight, ethnicity, history of hypertension, history of diabetes mellitus, cause of death, serum creatinine, hepatitis C serostatus, and whether donation occurred after circulatory death.
6. Record any and all immunosuppressive medication from induction to randomization as well as any other medications taken during the 10 days prior to randomization.
7. Randomization should occur as soon as possible after confirmation of qualifying viremia but not more than 10 days after the qualifying sample was collected. Dosing of study drug should occur as soon as possible after randomization.
8. In the event that a subject requires hemodialysis, plasmapheresis, or immunoabsorption treatments; if <15 days since last MAU868/placebo treatment another dose will be given as soon as possible, and the next scheduled monthly dose skipped. Regular dosing will occur the following month. If the last dose was 15 days or greater no interim dose will be administered and the regular monthly scheduled will be followed. No subject will receive more than 4 doses.
9. A sufficient amount of urine should be collected at each assessment to accommodate three tests; one for BKV DNA PCR, one for possible genotypic resistance testing and a back up sample. Refer to the study's Laboratory Manual for volume requirements.
10. On Study Day 1 collect samples for BKV PCR, antidrug antibodies, and safety labs prior to administration of first dose of MAU868. Refer to the study's Laboratory Manual for collection requirements.
11. After screening, plasma samples should be collected and sent to the central laboratory at each assessment for BKV DNA PCR, possible genotypic resistance testing and a backup sample. During screening, only BKV PCR is required and may be performed by the laboratory used by the site for usual clinical care, or sent to the central lab for testing. Refer to the study's Laboratory Manual for volume requirements.
12. In the event subject undergoes hemodialysis, plasmapheresis, or immunoabsorption treatment, a PK sample should be collected prior to and following the respective treatment.

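### The highest-dose and 1.4X margin statements hold only at 67.5 kg or above, and do not cover incomplete drug removal under the re-dosing rule

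*Protocol*

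**What the plan says.** Protocol Section 1.6 (repeated in the synopsis) describes "the highest administered dose of MAU868 expected in this study (6750 mg = 100 mg/kg for a 67.5 kg patient" and says this "was also the highest administered dose (MAU868 100 mg/kg) investigated in the first-in-human study". For monthly 6750 mg it gives a steady-state AUC of 1,031,155 µg·hr/mL, which "provides a safety margin of 1.4X compared to the NOAEL (750 mg/kg"; the rat AUC is 1,420,000 µg·hr/mL. Section 1.4.1 shows that the human experience is with single doses. Section 1.3 reports that the rats were dosed weekly and that 750 mg/kg was the highest IV dose given.

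Section 5.3 gives 6750 mg as a flat dose: all four infusions in Cohort 3, and Day 1 in Cohort 2. Sections 3.2.1 and 3.2.2 contain no weight criterion.

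For a subject who needs hemodialysis, plasmapheresis or immunoabsorption, Section 5.3.1 says "it shall be assumed that the study drug has been removed" and then "if <15 days since last MAU868/placebo treatment another dose will be given as soon as possible, and the next scheduled monthly dose skipped". Regular dosing resumes the month after, and "No subject will receive more than 4 doses". Appendix A footnote 8 and SAP Section 2.2.4 repeat the rule. PK samples are taken before and after the procedure, but Section 8.5.6 says PK results do not go to the site.

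**The concern.** Safety is the primary objective, and Section 1.6 is where the protocol justifies the 6750 mg infusions. Its two reassurances are that the dose is no higher than one already given to humans and that exposure lies below the rat NOAEL exposure. Both are worked at a single weight and on a regular monthly schedule.

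The protocol allows two departures that Section 1.6 does not discuss. One is a subject lighter than 67.5 kg. The other is a subject re-dosed within 15 days on an assumption of complete removal. The documents give no data for that assumption, no rule uses the PK samples before the re-dose, and the text does not say how it applies when sessions are repeated.

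SAP Section 7.3.6 summarises only days of exposure and number of doses, so neither a high mg/kg dose nor two doses close together would be visible in the exposure tables.

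**Working it through.** **The plan's own figures reproduce.** 6750/67.5 = 100 mg/kg. 1,420,000/1,031,155 = 1.377, stated as 1.4X. For 1350 mg, 1,420,000/206,231 = 6.89 and 1,031,155/206,231 = 5.00, stated as 6.9X and 5.0X.

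**Weight.** Dose in mg/kg is 6750/w. If clearance varies as weight to the power b, the Cohort 3 margin is 1.377 × (w/67.5)^b. The documents do not give b; b = 1 corresponds to the mg/kg conversion that the protocol uses.

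| Weight (kg) | mg/kg | Margin, b = 1 | b = 0.75 | b = 0 |
|---|---|---|---|---|
| 67.5 | 100 | 1.38 | 1.38 | 1.38 |
| 60 | 112.5 | 1.22 | 1.26 | 1.38 |
| 50 | 135 | 1.02 | 1.10 | 1.38 |
| 45 | 150 | 0.92 | 1.02 | 1.38 |

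The margin reaches 1.0 at 67.5/1.377 = 49.0 kg for b = 1, at 67.5/1.377^(1/0.75) = 44.1 kg for b = 0.75, at 67.5/1.377² = 35.6 kg for b = 0.5, and never for b = 0. At 1350 mg a subject would have to weigh under 1350/100 = 13.5 kg to exceed 100 mg/kg, so only the 6750 mg infusions are affected.

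**Re-dosing, Cohort 3 at 67.5 kg.** I used a one-compartment model with A = 1,031,155 per dose. The half-life is an assumption. The protocol's figures suggest about 25 days: the Cohort 3 end-of-treatment trough is 1264 × 0.093/0.137 = 858 µg/mL, against 509.8 µg/mL 28 days after one dose. The ratio is 1.683 = 1 + r + r², so r = 0.466 per 28 days and the half-life is 25.4 days. I show 20 to 30 days.

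Let k = ln 2/half-life and r = exp(−28k). Just after dose 3 the body holds S = 1 + r + r² doses. After a re-dose g days later with fraction f retained, it holds B = 1 + f·S·exp(−kg). The AUC over the 28 days from dose 3 is A × [S(1 − exp(−kg)) + B(1 − exp(−k(28 − g)))].

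Example, half-life 20 days, g = 2, f = 1: S = 1.522, exp(−kg) = 0.933 and B = 2.420. The AUC is A × [1.522 × 0.067 + 2.420 × 0.594] = 1.54A, and the margin is 1.377/1.54 = 0.89.

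Margin with full retention (f = 1), one re-dose after dose 3:

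| Half-life (days) | 2 days after | 7 days | 14 days |
|---|---|---|---|
| 20 | 0.89 | 0.94 | 1.04 |
| 25.4 | 0.98 | 1.03 | 1.13 |
| 30 | 1.05 | 1.11 | 1.22 |

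- Complete removal (f = 0): the largest 28-day AUC is 0.74 to 0.97 of A for one re-dose after dose 1 or dose 3. There is no excess.
- Half retained (f = 0.5), after dose 3: 0.92 to 1.15 of A. The excess begins at roughly this level.
- Full retention, after dose 1: 0.88 to 1.22 of A, a margin of 1.56 to 1.13.

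**The case against.** Several points on the other side stand.

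- Section 1.6 says openly that its conversion is for a 67.5 kg patient, and flat dosing is a legitimate design choice. The fault is that the comparison with the highest human dose is made for the study as a whole.
- The 1.4X figure describes monthly 6750 mg, so the margin point belongs to Cohort 3. Cohort 2 receives 6750 mg once.
- The interval of the rat AUC is not stated. If 1,420,000 covers one weekly interval, four weeks give 5,680,000 and the margin at 67.5 kg is 5,680,000/1,031,155 = 5.5X.
- There are safeguards. Exclusion 5 removes subjects likely to need these procedures, and Exclusion 13 allows exclusion for unacceptable risk. Cohort 3 opens only after unblinded safety and PK review of Cohorts 1 and 2. The DSMB and the pause rule also apply, and SAP Section 7.6 plans to relate PK to weight. These reduce the risk but do not supply the missing exposure statement.

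A reader might infer three stronger conclusions.

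- *Light subjects cross a toxic threshold.* The documents do not show this. 750 mg/kg is the highest IV dose reported in rats and was well tolerated, so a margin below 1 means leaving tested exposure.
- *All four Cohort 3 doses could be given within days.* This needs the rule to fire at every session, which sits badly with its own text: one further dose, the next monthly dose skipped, regular dosing the month after. An excess also needs poor removal. Four doses three days apart give a margin of 0.60 to 0.78X with full retention, but stay below 1,031,155 with complete removal.
- *The Cohort 2 re-dose could be either 6750 or 1350 mg.* Sections 4.1, 7.3.1 and 10.1 place 6750 mg once, on Day 1, with 1350 mg afterwards, and Section 5.3.1 adds "Dose adjustments and interruptions of study drug are not permitted". Only a cross-reference is missing.

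**Conclusion.** The weight point holds by arithmetic. The statement that no dose exceeds the highest tested in humans fails for every subject under 67.5 kg given 6750 mg, by 12.5%, 35% and 50% at 60, 50 and 45 kg. The effect on the Cohort 3 margin is uncertain, because it depends on an unstated weight exponent and an unstated rat AUC interval. Taking the protocol's rat AUC as directly comparable, the margin at 45 kg lies between 0.92X and 1.38X.

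The re-dosing point is conditional. Under the protocol's removal assumption the AUC behind the 1.4X margin is not exceeded. If about half or more of the drug is retained and earlier doses have accumulated, it can be; with full retention after dose 3 the margin is about 0.89 to 1.22X. A single re-dose is enough for this. The defect is an untested assumption and silence on repeated sessions, not a shown excess.

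**What to change.** - In Protocol Section 1.6 and the synopsis, replace the single-weight statement with mg/kg dose and margin across the weights that can be enrolled. State the clearance scaling and the interval of the rat AUC.
- Reconcile Section 5.3.1, Appendix A footnote 8 and SAP Section 2.2.4 with Section 1.6 on incomplete removal and on repeated sessions, and cross-refer to Sections 4.1 and 10.1 for the Cohort 2 dose. The dosing rule itself is for the sponsor and the DSMB.
- In SAP Section 7.3.6, add mg/kg per infusion and the highest 28-day cumulative mg/kg. Weight is already recorded at each infusion visit.
- Give the DSMB a listing of re-dosed subjects with their pre- and post-procedure PK.

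The cost is protocol wording, one table and one listing from data already collected. The stated margin may look less favourable for light subjects.

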5.3.2 Study Drug Compliance

All study drug will be administered at the clinical center, by qualified site staff, under the supervision of the Investigator or qualified designee. Any interruption to the IV infusion or changes to the infusion rate and duration must be recorded in the source documents and in the eCRF.

All study drug must be recorded in the Drug Accountability Log.

5.4 Storage and Accountability

The recommended storage condition of the drug product is 2-8°C, protected from light. The drug product should not be shaken or frozen. Details on the requirements for storage and management of study drug, and instructions to be followed for subject numbering, prescribing/dispensing and administering the study drug are outlined in the Pharmacy Manual.

6 PRIOR AND CONCOMITANT MEDICATIONS AND/OR PROCEDURES

6.1 Excluded Medications and/or Procedures

The following medications are excluded from use during this study and patients anticipated to require these interventions should not be included:

- Systemic mTOR inhibitors (e.g., rapamycin, sirolimus, everolimus, temsirolimus, etc.)
- IVIG
- antibody-depleting therapies (e.g., hemodialysis, plasmapheresis, immunoabsorption, etc.)
- any other investigational drug

If, after randomization, it is determined that these therapies are essential for the subject's health and well-being and cannot be delayed until study completion, the subject should not be discontinued from study medication or the study due to receipt of these medications. See [Section 5.3.1](#) and the Schedule of Events ([Appendix A](#)) for more information regarding dosing and PK collection in the event a subject requires hemodialysis, plasmapheresis, or immunoabsorption treatments.

